Aside from smoking cessation and physical exercise, there are currently no known effective medical treatments for patients with advanced non-surgically correctable CLI [13, 21]. In addition, the prevalence of amputations resulting from CLI among diabetic patients is disturbingly high [2]. Based on our recent preclinical studies, we are proposing a pilot clinical trial to further explore the potential therapeutic benefits of NAC in healing extremity amputation stumps in the setting of CLI, plus or minus diabetes. These studies are highly innovative in that they: i) explore a compelling new modality of therapy in a highly vulnerable, but frequently under-represented clinical trial patient population, ii) explore a completely novel and not previously reported NAC mechanism of action on phospholipid synthesis and expression, and iii) represent the potential use of a low-cost, generic pharmacological agent, which would otherwise not be pursued by drug pharmaceutical manufacturers due to low-profit margins. In short, this proposal may establish a conceptual infrastructure for future larger clinical trials exploring the use of NAC in patients with CLI and with and without diabetes, and identify a previously unknown novel mechanism of action for NAC.

We believe that previous literature supporting the role of NAC in augmenting compensatory tissue perfusion raises the possibility that this may be an advantageous therapeutic agent to favorably alter the tissue lipidomic profile of diabetic patients receiving NAC. We believe that NAC offers a new treatment strategy for patients with CLI undergoing lower extremity amputation with the intent to improve tissue perfusion, healing, and reduce morbidity and mortality associated with lower limb amputation.

Study Objectives

Primary Aim 1

Determine whether NAC can affect major lower extremity amputation stump perfusion by POD (Post-operative Day) 5

Primary Aim 2

Determine whether NAC can affect major lower extremity stump healing for 30 days following amputation.

Secondary Aim

Determine the effect size in diabetic patients that is necessary to power a larger clinical trial to determine whether NAC treatment can improve tissue perfusion and healing at major lower extremity amputation stumps.

Rationale for the Selection of Outcome Measures

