Upon consent and enrollment in the study, relevant subject information will be relayed to the Barnes Jewish Hospital (BJH) Investigational Pharmacy. Prior to proceeding to the operating room for lower extremity amputation, the patients will be randomized 1:1 by the BJH Investigational Pharmacy to either placebo saline infusion (twice daily) or a standard adult intravenous dose of NAC (1200mg twice daily) for 6 days post-amputation during the usual post-operative inpatient extremity off-loading and stump monitoring period. The pharmacy will maintain blinding, with no member of the investigational team having access to the record until the conclusion of the trial.

Early Withdrawal of Subjects

Patients unable to tolerate the administration of the drug will be withdrawn from the study at any point during their hospitalization and will continue to be monitored until their condition stabilizes. Patients unable to participate in the Post-operative Day 0 Non-invasive Laser Assisted Fluorescence Angiography (LAFA) will be withdrawn from the study at that time point and will not receive the investigational product. Subjects for which continuous IV access is not medically indicated during the 6 day study drug administration period may be withdrawn from the study. Patients unable to participate in follow-up appointments will also be withdrawn from the study.

When and How to Withdraw Subjects

Patients unable to tolerate the administration of the drug will be withdrawn from the study trial at any point during their hospitalization. Patients unable to participate in follow-up appointments will also be withdrawn from the study. They will continue to be monitored for adverse events as inpatients for the duration of their hospitalization. Patients unable to participate in the Post-operative Day 0 Non-invasive Laser Assisted Fluorescence Angiography (LAFA) will be withdrawn from the study at that time point and will not receive the investigational product. No further study follow up will be required.

Data Collection and Follow-up for Withdrawn Subjects

Patient data will be collected up until time of withdrawal from the study and pooled into the collective analysis along with all other patients.

Study Drug

Description

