N-acetyl cysteine (NAC) ((2R)-2-acetamido-3-sulfanylpropanoic acid) is an amino acid derivative of L-cysteine, which is a precursor to glutathione and cysteine. Historically, NAC has been used to treat acetaminophen overdose [6], as well as mucous secretions in patients with cystic fibrosis or chronic obstructive pulmonary disease [24].

Pharmacokinetics including the following [24] :

Distribution: The steady-state volume of distribution (V_{dss}) and the protein binding for acetylcysteine were reported to be 0.47 liter/kg and 83%, respectively.

Metabolism: N-acetyl-cysteine may form cysteine, disulfides, and conjugates in vivo (N, N'-diacetylcysteine, N-acetyl cysteine-cysteine, N-acetyl cysteine-glutathione, N-acetyl cysteine-protein, etc). Based on published data, it was reported that after an oral dose of 35S-acetylcysteine, about 22% of total radioactivity was excreted in urine after 24 hours. No metabolites were identified.

Elimination: After a single intravenous dose of N-acetyl cysteine, the plasma concentration of total N-acetyl cysteine declined in a poly-exponential decay manner with a mean terminal half-life (T_{1/2}) of 5.6 hours. The mean clearance (CL) for N-acetyl cysteine was reported to be 0.11 liter/hr/kg and renal CL constituted about 30% of total CL.

Treatment Regimen

Upon study enrollment, patients will be randomized 1:1 by BJH Investigational Pharmacy to either placebo ½ normal saline infusion (twice a day) or a standard adult intravenous dose of NAC (1200mg twice a day) for 6 days post-amputation. The BJH Investigational Pharmacy will perform this with knowledge of the patient's medical record number (MRN), and without knowledge of any pre-existing medical conditions, comorbidities, past medical history, prior interventions, etc. The first infusion will be administered within three hours from leaving the operating room. The second infusion will be a minimum of 6 hours after the first infusion, or at 21:00 in an attempt to be consistent with routine hospital BID dosing times. Patients will receive their scheduled infusions as long as they are hospitalized according to the chart below (Table 1). **If medication is not administered within that window, dose will not be given to not interfere with the rest of the doses.**

Table 1:

Post-operative Day (POD)	Infusion Schedule
POD 0	1. Within 3 hours from the conclusion of the operation 2. Approximately 6 hours after first infusion, or at 21:00 +/- 6 hours

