POD 1	1. 9:00 +/- 6 hours 2. 21:00 +/- 6 hours
POD 2	1. 9:00 +/- 6 hours 2. 21:00 +/- 6 hours
POD 3	1. 9:00 +/- 6 hours 2. 21:00 +/- 6 hours
POD 4	1. 9:00 +/- 6 hours

	2. 21:00 +/- 6 hours
POD 5	1. 9:00 +/- 6 hours 2. Anticipated discharge, second infusion may be given if patient is still inpatient or missed any doses

Preparation and Administration of Study Drug

All investigational doses will be prepared by the research pharmacy and prepared in a manner that both active and placebo doses appear identical to protect the blind. Preparation of each dose will be performed using aseptic technique, and within a laminar flow hood. Each dose will be a total volume of 50 mL and will be administered over a period of 30 minutes through an IV. N-acetyl-cysteine will not be infused in the same intravenous line as iron-products, cefepime, or ceftazidime.

Subject Compliance Monitoring

The Barnes-Jewish Hospital inpatient electronic medication administration record (eMAR) will be used to assess compliance; significant patient noncompliance, defined as refusal or inability to adhere to the protocol requirements, will lead to subject withdrawal.

Prior and Concomitant Therapy

Use of any investigational agent within 30 days before the first dose of study drug and until after the last evaluation will not be allowed. Since concomitant use of N-acetyl-cysteine and carbamazepine may cause decrease carbamazepine plasma concentrations resulting in an increased risk of seizures, patients who are receiving carbamazepine will not be enrolled in the study.

Concurrent use of N-acetyl-cysteine and nitroglycerin may result in enhanced hypotension and nitroglycerin-induced headache. Therefore patients who receive both agents will be monitored by members of the study team for any potential anticipated complications.

All other concomitant medications that are necessary for the health and well-being of the patient that are not specifically prohibited by the protocol are permitted.

Packaging

Acetadote (acetyl-cysteine) Injection is available as a 20% solution (200mg/mL) in 30 mL single dose glass vials. Acetadote is sterile and can be used for I.V. administration.

Blinding of Study Drug

All intravenous doses will be prepared in identical evacuated IV containers with a total volume of 50mL. N-acetyl cysteine is a clear and colorless solution, and no additional blinding material will be required.

Receiving, Storage, Dispensing and Return

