2. Clean the selected measuring site with alcohol or other skin-preparation solution.
3. Dry the site well with a gauze pad.
4. Take a standard fixation ring.

5. Remove the fixation ring from the protective film.

6. Apply the fixation ring to the measuring site as follows:
 - Press the center of the fixation ring onto the measuring site with a finger.
 - Run a finger around the rim circumference.

Note: Press firmly to prevent leaks.

7. Fill the hole in the fixation ring with 3-5 drops of the contact liquid.

8. Affix the electrode into the fixation ring as follows:
 - Align the arrow on the electrode with one of the marks on the fixation ring.
 - Turn the electrode 90° clockwise to fasten it in the fixation ring.

9. Repeat steps 1 to 8 if more electrodes are to be applied.

Wait for a stable reading after the electrode has been affixed to the patient.

Note: The physiological stabilization time of a patient is 15-20 minutes for the tcpO₂ reading. During this time the electrode will slowly heat the skin, making the arteries dilate. Longer time may indicate an incorrect attachment of the electrode or a poorly selected measuring site.

C. Anthropometric Measurements

Location of Procedure:

- Barnes-Jewish Hospital Operating Rooms
- Inpatient Hospital Units
- Other Hospital Units also housing vascular surgery patients

Measurements:

Measurements will be collected as long as the patient is hospitalized, including:

1. Temperature (daily maximum and minimum)
2. Blood Pressure Range

3. Heart Rate Range
4. SpO₂ Range
5. Respiratory Rate Range
6. Amputation wound assessment on POD 3 (if stump dressings are off and still hospitalized) and POD 5 (if stump dressings are off and still hospitalized).

In addition, a blood sample (~50mL; 3-4 table spoons) may be obtained for:

1. Hospital laboratory evaluations that may be obtained per standard of care, at standard of care time points during the hospital stay

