2. The patient is scanned under an existing non-contrast MRI protocol to obtain blood flow and tissue oxygenation pictures at rest.

3. Each study patient is carefully monitored by a physician, nurse practitioner, physician assistant or nurse for signs and symptoms of allergic reaction or intolerance to this non-invasive procedure until discharge.

Visit 1

Following patient discharge, amputation stumps will be evaluated within 20-50 days during a routine post-operative visit using the same anthropometric parameters (LAFA and TcPO₂ will not be performed at this time point).

Safety and Adverse Events

Safety and Compliance Monitoring

All study patients are inpatients at BJH in St. Louis Missouri and are cared for by appropriately trained nurses on the inpatient wards. Vascular surgery Attending Physicians, Vascular Surgery Fellows, Surgical Residents, and a team of Nurse Practitioners oversee their overall care. Inpatient ward nurses routinely assess patients at least every 4 hours with vital signs, intake and output measurements, pain assessment, nutrition assessments, medication review and administration, etc.

Medical Monitoring

Medical monitoring of the study will be performed by the Principal Investigator. The goal of monitoring this study is to enhance human subject protection and to monitor the quality of the clinical trial data by focusing investigator oversight on the most important aspects of study conduct and reporting. The PI will provide regular oversight to ensure adequate protection of the rights, welfare, and safety of the human subjects and the quality of the clinical trial data.

Definitions of Adverse Events

An adverse event (AE) is defined as any untoward medical occurrence in a subject administered a pharmaceutical product or who has undergone study procedures and which does not necessarily have a causal relationship with this treatment. An AE can therefore be any unintended sign (including an abnormal laboratory finding), symptom, or disease temporally associated with the use of the investigational product, whether or not related to the medicinal (investigational) product.

All AEs will be recorded in the CRF from the time of consent through the 30 days post-operative visit. AEs will be followed to resolution or stabilization.

An abnormality identified during a medical test (e.g., laboratory parameter, vital sign, physical exam) should be defined as an AE only if the abnormality meets one of the following criteria:

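### Patients who cannot tolerate study drug or are significantly noncompliant leave the study itself, so their post-discharge stump assessment (Primary Aim 2) is not collected, while missing outcomes are declared not applicable despite a 10% dropout allowance

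*Combined protocol and SAP*

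**What the plan says.** The protocol section When and How to Withdraw Subjects reads: "Patients unable to tolerate the administration of the drug will be withdrawn from the study trial at any point during their hospitalization". Subject Compliance Monitoring adds that "significant patient noncompliance, defined as refusal or inability to adhere to the protocol requirements, will lead to subject withdrawal". Early Withdrawal of Subjects adds a discretionary route: "Subjects for which continuous IV access is not medically indicated during the 6 day study drug administration period may be withdrawn from the study". A single late dose is different. Under Treatment Regimen it is skipped and the patient stays in: "If medication is not administered within that window, dose will not be given to not interfere with the rest of the doses".

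Data Collection and Follow-up for Withdrawn Subjects applies to everyone who is withdrawn: "Patient data will be collected up until time of withdrawal from the study and pooled into the collective analysis along with all other patients".

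Primary Aim 2 is to "Determine whether NAC can affect major lower extremity stump healing for 30 days following amputation". The only assessment after discharge is Visit 1: "Following patient discharge, amputation stumps will be evaluated within 20-50 days during a routine post-operative visit using the same anthropometric parameters". Before that there are inpatient checks under Anthropometric Measurements: "Amputation wound assessment on POD 3 (if stump dressings are off and still hospitalized"; POD 5 carries the same conditions.

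Sample Size Determination and Power, in both protocol and SAP, plans 25 patients per group with a 10% dropout allowance. Missing Outcome Data, in both, is marked not applicable.

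**The concern.** No section separates stopping study drug from leaving the study. Taken together, the withdrawal and data-collection rules mean that a patient who stops drug in hospital, through intolerance or significant noncompliance, is never assessed at Visit 1 for the trial. What remains is any POD 3 or POD 5 wound check made before withdrawal, and neither shows healing to 30 days.

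The withdrawal follows randomisation, and its cause may be the drug. Dose Rationale and Risk/Benefits lists skin reactions as the leading effects of intravenous NAC, and the comparator is saline. The healing comparison would then be made among those who stayed, who need not be alike in the two arms.

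Healing is one of two primary aims. The Secondary Aim also seeks an effect size for healing as well as perfusion, so any distortion would carry into the design of the next trial. A plan that budgets for dropout but declares missing outcomes not applicable gives the analyst no assumption, method or reporting rule for the loss it expects.

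**Working it through.** **Inputs from the documents.** 25 per group and 10% dropout (Sample Size Determination and Power). 40% re-amputation or revision (Study Abstract), used here only as an illustrative failure rate.

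**Assumptions.** The healing endpoint is not defined, so a yes/no failure outcome is assumed. All dropouts are charged to the withdrawal rules, which is the extreme case.

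**The plan's own figure.** 25 per group cannot be derived, because no alpha, power, effect size or SD is given. As arithmetic, 25 × 0.90 = 22.5 and 22 / 0.90 = 24.4, which rounds up to 25. The plan therefore implies about 22 evaluable patients per group. 10% of 25 = 2.5, so k = 2 or 3 lost per arm.

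**Loss in both arms, equal observed failure counts x.** With a and b unseen failures (each 0 to k), the difference, NAC minus placebo, is (x + a)/25 − (x + b)/25 = (a − b)/25.
- k = 2: −2/25 to +2/25 = ±8 points.
- k = 3: −3/25 to +3/25 = ±12 points.

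**Loss on NAC only, equal observed failure rates r, placebo complete.** The difference is [r(25 − k) + a]/25 − r = (a − rk)/25, with a from 0 to k.
- r = 0.40, k = 2: (0 − 0.8)/25 to (2 − 0.8)/25 = −3.2 to +4.8 points.
- r = 0.40, k = 3: (0 − 1.2)/25 to (3 − 1.2)/25 = −4.8 to +7.2 points.
- r = 0.20, k = 3: (0 − 0.6)/25 to (3 − 0.6)/25 = −2.4 to +9.6 points.
- r = 0.60, k = 3: (0 − 1.8)/25 to (3 − 1.8)/25 = −7.2 to +4.8 points.

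The width is always k/25, that is 8 or 12 points; only its position depends on r.

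**Sampling error for comparison.** The 95% half-width is 1.96 × √(2p(1 − p)/n).
- p = 0.2, n = 25: 1.96 × 0.113 = 22 points.
- p = 0.4, n = 23: 1.96 × 0.145 = 28 points.
- p = 0.5, n = 22: 1.96 × 0.151 = 30 points.

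**Timing.** Visit 1 is counted from discharge, Aim 2 from amputation. If discharge is on POD 5, as Table 1 anticipates, Visit 1 falls 25 to 55 days after amputation (5 + 20 to 5 + 50). It is the nearest available measure of 30-day healing, not an exact one.

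**The case against.** The strongest reply is that little may be lost. The trial is an unpowered pilot. Dose Rationale and Risk/Benefits calls side effects rare, and Clinical Data to Date says NAC was well tolerated in other trials. The 10% allowance covers every cause, and patients who cannot attend follow-up would miss Visit 1 under any rule. All of this stands, and it limits the size of the point. It does not remove the gap in the text.

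A second reply is that the analysis already copes, since data up to withdrawal are pooled and a GEE or mixed model is named. For perfusion this is partly right, and Aim 1 is affected less. But no missing-data assumption is stated. The D0 LAFA is taken in the operating room before the first infusion, so withdrawal before POD 3 leaves no post-dose LAFA value. Neither model supplies a healing assessment that was not collected.

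A reader might also infer more than the documents support:
- *That losses will fall mainly on NAC.* A list of leading side effects ranks them and gives no frequency. Differential loss is possible, not shown. A one-sided range of 0 to +8 or 0 to +12 points would come from assuming equal failure counts in arms of unequal observed size, which already builds in a worse rate on NAC.
- *That the outcome is beyond recovery.* Visit 1 is a routine clinical visit, so many withdrawn patients may be examined anyway. What is missing is a provision to record that result for the trial.
- *That withdrawn patients' adverse events go unrecorded.* The protocol records adverse events through the 30-day visit, and Early Withdrawal of Subjects keeps intolerant patients under observation until stable.
- *That all withdrawn patients are released from follow-up.* The sentence saying so directly follows the one on a missed POD 0 LAFA and may concern only those patients.

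**Conclusion.** The point holds on the text. Patients withdrawn in hospital for intolerance or significant noncompliance lose the only post-discharge measure for Primary Aim 2, for a reason that arises after randomisation and could depend on arm. The not-applicable entry contradicts the plan's own dropout allowance. Neither conclusion depends on an assumed healing rate.

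The size is modest. At the extreme, with all 2 or 3 losses per arm due to these rules and a yes/no endpoint, the difference is undetermined by ±8 or ±12 points. With loss on NAC only and equal observed rates of 40%, the range is −3.2 to +4.8 or −4.8 to +7.2 points. These are bounds, not expected bias, and they are smaller than sampling error at this sample size. The true share could be close to zero. The matter should be fixed because the remedy is cheap and preserves a primary outcome, not because serious bias has been shown.

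**What to change.** 1. **Separate stopping study drug from leaving the study.** Unless consent is withdrawn, record the stump outcome at the routine Visit 1, or from the chart if the patient cannot attend. Screening for Eligibility allows outside records for screening and patient care; extend the protocol wording, and the consent wording if needed, to this research use. Analyse healing in all patients as randomised.
2. **Replace the not-applicable entry in protocol and SAP.** For perfusion, use the mixed model already named, fitted by likelihood under a stated missing-at-random assumption. State separately that patients withdrawn undosed for lack of a POD 0 LAFA have no D0 value; report them by arm and leave them out of the perfusion model, which is acceptable because that withdrawal precedes dosing. Report numbers missing by arm and a simple sensitivity analysis for healing, such as the bounds above once the endpoint is defined.
3. **Minor wording.** Reconcile the withdrawal sections (inpatient monitoring, observation until stable, release from further follow-up) with the adverse-event sections that record events through the 30-day visit. Say to whom the release applies.

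The clinical criteria for stopping drug are left as they are, and the sample size does not change. The cost is protocol, SAP and possibly consent wording, plus a few extra visit or chart records. Some outcomes will still be missing, and item 2 covers those.

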- **Postoperative Day5:** Obtained at the bedside in the inpatient hospital unless the patient is discharged.

Contraindications to LAFA:

- Patient refusal/inability to precipitate in measurement before or during data collection.

- Allergic reaction previously documented to Indocyanine green (ICG) fluorescent dye (*a contraindication to LAFA does not exclude the patient from other measurements within the study protocol*).
- Patient unable to lie supine and immobile for at least 10 minutes during the imaging procedure.
- End-stage liver disease
- Severe clinical asthma

LAFA Procedural Steps:

1. Each patient is entered into the Novadaq SPY *Elite*[®] computer system, with pre-set optimized settings for appropriate visualization for LAFA.
2. Utilizing a standard protocol per the manufacturer (Novadaq SPY *Elite*[®] system), a 7.5mg (3mL) solution of ICG (reconstituted with sterile saline) is injected intravenously into each patient.
3. The patient is asked to lie supine, immobile for a period of approximately 10 minutes
4. The device is placed over the limb/amputation stump being studied and centered to allow full visualization of the entire stump
 - a. Prop up and immobilize stump
 - b. Obtain a still color image of the stump
 - c. Start an image buffering time of between 10-30 seconds
 - d. ICG is intravenously injected by the patient's nurse or a member of the study team.
 - e. ICG injection is followed by a 10mL of sterile saline flush in the same intravenous line.
 - f. A member of the study team will obtain LAFA imaging of the stump for a total of 150-180 seconds.
 - g. All study images will be stored on the Novadaq SPY *Elite*[®] system hard drive. Study images, including only the study ID and date of exam, will be loaded onto a jump drive and then immediately downloaded onto the WUSTL Department of Surgery/Vascular network drive. The images will then be deleted from the jump drive..
5. Each study patient will be carefully monitored by a physician, nurse practitioner, physician assistant or nurse for signs and symptoms of allergic reaction or intolerance to this non-invasive procedure until discharge.

B. Measurement of Transcutaneous Oxygen Pressure (TcPO₂)

Location of Procedure:

- Barnes-Jewish Hospital Operating Rooms
- 4400/8300/7400/7500 Inpatient Hospital Units
- Other Hospital Units also housing vascular surgery patients

Time of Data Collection:

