All AEs will be recorded in the CRF from the time of consent through the 30 days post-operative visit however all AEs will be followed to resolution or stabilization.

Study Outcome Measurements and Ascertainment

As described previously, study subjects will undergo evaluations using LAFA, TcP02, and anthropometric measurements.

Statistical Plan

Sample Size Determination and Power

The purpose of this study is to obtain sufficient preliminary data to determine the sample size necessary for a future large definitive clinical trial. For this pilot study, we plan to enroll 25 patients in each group, allowing for a dropout rate of 10% per group.

We emphasize that effect size (the expected difference in primary outcome between the treatment and control groups) should not be determined by the pilot study. Rather it is determined by the minimum clinically important difference. However, the effect size from the pilot give us some ideas about possible achievable difference.

Interim Monitoring and Early Stopping

An interim analysis will be conducted once >30 patients are enrolled in the study. Analysis will focus on determining differences between NAC and control group. Interim analysis will help determine early differences between the study groups and safety profile of study intervention. The investigators may end the study early depending on study findings, safety profile of the data, and/or if data is adequate for a peer-reviewed publication.

Analysis Plan

Data analysis include (1) the partition of variation of outcome measurements into within and between patient components to obtain standard deviation of measurements, intra-class correlation of the measurements, (2) use of appropriate regression model (GEE or mixed effect regression) to compare the outcome measurements between two groups, while accounting for the intra-class correlation. Interpretation of analysis should be made within the context of a pilot study where we have a pre-specified hypothesis but do not have power analysis for testing the hypothesis.

Statistical Methods

One of the main study outcomes (and in the future large study) is the stump perfusion assessment, which is a continuous variable measured three times (D0, D3, and D5) after

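### The withdrawal rules conflict with the adverse-event rules on how long AEs are recorded after a patient is withdrawn

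*Combined protocol and SAP*

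**What the plan says.** Two parts of the protocol set the period for AE data.

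**The AE sections.** Under Definitions of Adverse Events the rule is: "All AEs will be recorded in the CRF from the time of consent through the 30 days post-operative visit". It is stated again later in that section, and Post-study Adverse Event repeats it with the follow-up of open events: "through the 30 days post-operative visit however all AEs will be followed to resolution or stabilization". None of these statements excepts withdrawn patients.

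**The withdrawal sections.** These give withdrawn patients several other end points:
- Early Withdrawal of Subjects: patients who cannot tolerate the drug "will continue to be monitored until their condition stabilizes".
- When and How to Withdraw Subjects, after the rules on intolerance and missed follow-up appointments: "They will continue to be monitored for adverse events as inpatients for the duration of their hospitalization".
- Same section, on patients who cannot have the POD 0 LAFA: they "will be withdrawn from the study at that time point and will not receive the investigational product. No further study follow up will be required".
- The section that comes next, on data collection after withdrawal, sets a further limit: "Patient data will be collected up until time of withdrawal from the study and pooled into the collective analysis along with all other patients".

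LAFA procedural step 5 adds a separate observation rule that runs until discharge: "Each study patient will be carefully monitored by a physician, nurse practitioner, physician assistant or nurse for signs and symptoms of allergic reaction".

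**The concern.** One set of rules runs to about day 30 for everyone. The other ends at discharge, or at withdrawal itself, for patients who leave the study. A coordinator cannot obey both, and the protocol does not say which prevails.

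Patients who could not tolerate the infusion are among those withdrawn, so the shorter rule would apply to a group that matters for safety. Safety is part of the trial's stated purpose (Purpose of the Study Protocol). The interim analysis after more than 30 enrolments looks at the safety profile, and the investigators may end the study on it (Interim Monitoring and Early Stopping, in both protocol and SAP). The principal investigator is the medical monitor and decides on continuation, and the Committees entry is not applicable. The plan therefore names no committee that would notice a shortened AE record.

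**Working it through.** The documents state no figure for AE observation time, so there is none to reproduce. The check compares the rules and then sizes the gap.

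**Step 1: which end points conflict.**
- *Until the condition stabilizes* has no calendar end and agrees with following AEs to resolution or stabilization. It does not conflict for the event that led to withdrawal.
- *The hospital stay* conflicts for new AEs that start after discharge.
- *No further follow-up after a missed POD 0 LAFA* conflicts with recording to the 30-day visit. It also sits badly with LAFA step 5, which observes every study patient until discharge.
- *Data up to withdrawal* is the strictest wording and conflicts with all the others.
- Withdrawal because IV access is no longer indicated (Early Withdrawal of Subjects) or for noncompliance (Subject Compliance Monitoring) has no AE rule of its own.

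The clear gap is therefore new AEs between discharge and day 30.

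**Step 2: inputs for an illustration.**
- AE window after surgery: W = 30 days (AE sections).
- Last observed day: d = 5, the anticipated discharge day in the infusion schedule (Table 1). Actual discharge may differ.
- Planned sample: N = 50, at 25 per arm. Dropout allowance: 10% (Sample Size Determination and Power).
- Assumption: the whole allowance consists of withdrawals handled under the shorter rule, so k = 0.10 × 50 = 5.

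**Step 3: loss per withdrawn patient.** (W − d)/W = (30 − 5)/30 = 25/30 = 83%.

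**Step 4: loss across the trial.** k(W − d)/(N × W) = (5 × 25)/(50 × 30) = 125/1,500 = 8.3% of planned AE person-days. The number withdrawn is unknown, so a range helps:
- k = 3: 75/1,500 = 5.0%
- k = 10: 250/1,500 = 16.7%

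**Step 5: is day 30 itself fixed?** Visit 1 takes place 20 to 50 days after discharge. With discharge on POD 5 that is POD 5 + 20 = 25 to POD 5 + 50 = 55. A rule ending at a 30-day visit therefore has no single calendar end, even for patients who stay in the study.

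**The case against.** The strongest reply is that the AE sections cover all AEs without exception, and that the in-hospital sentence sets a minimum of active monitoring rather than a limit on recording. On that reading nothing is lost. It is a possible reading, but it does not dispose of the sentence that stops data at withdrawal or of the one that requires no further follow-up.

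Several other objections stand and limit the point:
- **The triggering reaction.** The stabilization sentence and the AE sections agree, so the event that caused withdrawal is likely to be recorded and followed. The exposure is to later, new events.
- **ICG.** A reader might infer that a patient who reacts to ICG at the POD 0 LAFA leaves follow-up at once, with the whole 30-day window lost. The documents do not support this. The rule concerns patients who cannot take part, and many reasons for that (refusal, inability to lie still) can arise before any injection. Known ICG allergy is an exclusion. LAFA step 5 keeps every study patient under observation until discharge. These patients also receive no study drug, so their data carry no information about reactions to NAC.
- **Bias.** A reader might infer that the safety comparison is biased towards NAC. The section Dose Rationale and Risk/Benefits names rash, urticaria and pruritus as the usual complaints with IV NAC, and the comparator is saline, so more intolerance on NAC is plausible. However, that section also calls side effects rare, treatment is blinded, and no rates by arm are given.
- **Number of patients.** Five is the whole dropout allowance, not an estimate of patients withdrawn for intolerance. The protocol lists other reasons for withdrawal and gives no split.

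**Conclusion.** The conflict is real and lies in stated rules, not in missing detail. If the withdrawal text is followed, new AEs after discharge are not recorded in withdrawn patients, including those who could not tolerate the infusion.

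The trial-wide size is modest: about 8% of planned AE person-days, given a 30-day window, discharge on POD 5, and the whole 10% allowance being such withdrawals. Per withdrawn patient it is large, at about 83% of the window. If intolerance proves more common on NAC, the comparison would tend to favour NAC, but that direction is an inference.

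The text should be reconciled because safety is a stated purpose and feeds the interim decision. The stump outcomes are not at issue here.

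**What to change.** Reconcile the withdrawal sections with the AE sections by replacing the conflicting statements on data after withdrawal, including the one that stops data at withdrawal, with a single data-collection rule:
- Withdrawal from study drug or study procedures does not end AE recording. AEs are recorded to the same end point as for every other subject and followed to resolution or stabilization, unless consent for data collection is withdrawn.
- The source is the routine post-operative visit where the patient attends, and otherwise the hospital chart or outside records. Screening for Eligibility already permits outside records for screening and follow-up care. State explicitly that they may also be used for AE collection, since some patients are withdrawn precisely because they cannot attend.
- Give the calendar end of AE recording, and reconcile it with the Visit 1 window.

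This changes data collection only. The criteria for withdrawal and for stopping study drug are untouched. The cost is protocol wording and a little chart abstraction for a few patients, with no new procedure.
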